5.2.2. Main analytical approach

A primary objective is to determine parent GSK3640254 and total drug-related radioactivity systemic concentrations following a single IV microtracer dose of [¹⁴C]-GSK3640254 (with an oral dose of non-radiolabelled GSK3640254) and oral dose of [¹⁴C]-GSK36402541. To assess this, the plasma PK parameters: AUC(0–inf), AUC(0–t), C_{max}, t_{max} and t_{1/2} of parent and total drug-related material (radioactivity) will be summarized and listed. The volume V_{ss} and clearance (CL) of parent after IV dose (Period 1 only), renal clearance of parent (CL_r) after both IV and oral dose, oral clearance (CL/F) and apparent volume of distribution (V_z/F) for the parent following oral administration will also be summarized and listed.

To assess the absolute oral bioavailability of GSK3640254 absolute oral bioavailability (F), F_h, F_a and F_g will be summarized and listed.

To determine the rate and extent of excretion of total radioactivity in urine and feces and the total recovery of radioactivity, following IV and oral administrations of [¹⁴C]-GSK3640254 the PK parameters: Ae and Fe% will be summarized and listed for urine faeces and total (Urine + Faeces)

Table 6 Statistical methodology specification

The following pharmacokinetic statistical analyses will only be performed if sufficient data is available (i.e. if participants have well defined plasma profiles).

Pharmacokinetic Statistical Analyses (Absolute Bioavailability assessment in Treatment Period 1)
Primary Endpoint / Variables

 AUC(0-t), AUC (0-∞) PK parameters of Plasma GSK3640254 (radiolabeled/non-radiolabeled) from IV and oral dose in Period 1 will be analyzed after log_e transformation (PK parameters should be divided by corresponding dose)
Model Specification

 Will be statistically analyzed using a mixed model (MM) for Period1. Terms fitted in the mixed effect ANOVA model will include: 
 Fixed effect : Treatment (IV dose/Oral dose in Period1) Random Effect : Subject The Kenward and Roger method for approximating the denominator degrees of freedom and correcting for bias in the estimated variance-covariance of the fixed effects will be used. Point estimates for the adjusted means on the loge scale, the mean difference between treatments and associated 90% confidence interval for the contrast (test-reference) will be constructed using the residual variance.
Model Checking & Diagnostics

 Dose normalized PK parameters should be used for the analysis. For the Mixed Model analysis, Model assumptions will be applied, but appropriate adjustments maybe made based on the data. Distributional assumptions underlying the model used for analysis will be examined by obtaining a normal probability plot of the residuals and a plot of the residuals versus the fitted values (i.e. checking the normality assumption and constant variance assumption of the model respectively) to gain confidence that the model assumptions are reasonable. If there are any departures from the distributional assumptions, alternative transformations, such as data squared, or square root of data, will be explored.
Model Results Presentation

 The point estimate and confidence interval obtained from MM analysis will be exponentially back transformed to obtain Adjusted (least square) geometric means for each treatment. Point estimates (Absolute Bioavailability of GSK3640254) and associated 90% confidence interval for the ratio IV dose/Oral dose along with within-subject variability (%CVw) will be reported. Plots showing the adjusted geometric mean ratio(F) of IV dose to Oral dose in Period1 for AUC (0-∞) and AUC(0-t) together with 90% confidence intervals will be provided.

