3. SAMPLE SIZE DETERMINATION

No formal sample size calculation has been performed for this study. However, the sample size reflects an accepted industry standard for human ADME studies using ¹⁴C radiolabelled drug. Additionally, the design of the study in terms of the concomitant administration of intravenous with oral administration (Period 1) inherently reduces variability in the parameters determined, versus a cross-over design for absolute bioavailability assessment, while enabling cross-over to Period 2 in the same participants. The primary objective of the study is to gain a better understanding of the compound's pharmacokinetic, excretory, and metabolic profile and 4 to 6 participants are deemed sufficient for this purpose. Six participants will be enrolled into the study. To minimize the number of participants exposed to radiation; those participants that discontinue early will not be replaced unless the total number of participants who complete both Periods 1 and 2 drops below 4.

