5.2.1.2. Derived Pharmacokinetic Parameters**5.2.1.2.1. Derived plasma pharmacokinetic parameters**

PK Parameters will be calculated by standard non-compartmental analysis according to current working practices and using the currently supported version of WinNonlin version 6.3 or above. All calculations of non-compartmental parameters will be based on actual sampling times. PK parameters listed will be determined from plasma GSK3640254, [¹⁴C]-GSK3640254, total radioactivity as data permits and unless otherwise stated.

Table 4 Derived Pharmacokinetic Plasma Parameters

Parameter	Parameter Description
AUC(0-t)	Area under the concentration-time curve from time zero to the time of the last quantifiable concentration (C(t)) will be calculated using the linear trapezoidal rule for each incremental trapezoid and the log trapezoidal rule for each decremental trapezoid.
λ_z	The first order rate constant associated with the terminal (log-linear) portion of the concentration-time curve.
AUC(0- ∞)	Area under the concentration-time curve extrapolated to infinity will be calculated as: $AUC(0 - \infty) = AUC(0 - t) + \frac{C(t)}{\lambda_z}$
%AUCex	The percentage of AUC (0- ∞) obtained by extrapolation (%AUCex) will be calculated as: $\frac{[AUC(0 - \infty) - AUC(0 - t)]}{AUC(0 - \infty)} * 100$
Cmax	Maximum observed concentration, determined directly from the concentration-time data.
tmax	Time to reach Cmax, determined directly from the concentration-time data.
t _{1/2}	Apparent terminal half-life will be calculated as: $t_{1/2} = \ln 2 / \lambda_z$
CL	Total clearance calculated as: $CL = \frac{Dose(IV)}{AUC(0 - \infty)}$ Treatment Period 1, analyte [¹⁴ C]-GSK3640254 only and where the Dose(IV) is the actual IV dose provided by Covance, Harrogate
Vss	Volume of distribution at steady-state, calculated as:

Parameter	Parameter Description
	$V_{ss} = CL * MRT_{iv}$ 
Where CL is total clearance and MRT is the mean residence time, calculated as AUMC(0-∞) [Area under the first moment curve]/AUC(0-∞)

CLr	
If plasma AUC(0-∞) is calculable, then
 $CLr = \frac{\text{Cumulative Ae[Urine] for Period 1}}{\text{Plasma AUC}(0 - \infty)}$ 
If plasma AUC(0-∞) is not calculable, then
 $CLr = \frac{\text{Cumulative Ae[Urine] for Period 1}}{\text{Plasma AUC}(0 - t)}$ 
Where cumulative urine Ae from excretion data for treatment Period 1 and AUC from NCA PK analysis of Treatment Period 1, analyte [¹⁴C]-GSK3640254 only

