In case there is a problem with model convergence, the arithmetic means for \log_e -transformed $AUC_{(0-t)}$ and C_{max} and the treatment differences (85 mg suspension and 200 mg tablet) within each participant will be calculated using only data from the participants who have completed both the periods for 85 mg suspension and 200 mg tablet. The mean treatment difference and paired-t test based 90% CIs for treatment difference in \log_e scale will be estimated. The results will be provided in an exponentially back-transformed scale.

Model Results Presentation

Based on the relative bioavailability, the bioequivalence between 85 mg suspension and 200 mg tablet will be evaluated as follows:

- The bioequivalence is established when the 90% CI of the ratio for $AUC_{(0-t)}$, $AUC_{(0-inf)}$ and C_{max} between treatment formulations (85 mg suspension and 200 mg tablet) are within the range of 0.80 to 1.25.

5.5. (Other) Safety Analyses

The safety analyses will be based on the Safety analysis set, unless otherwise specified.

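### With 4 to 6 men, the SAP Table 6 model for absolute bioavailability has no complete-pair rule and no rule for a zero subject variance, so its 90% CI can become the unpaired, narrower one

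*SAP*

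**What the plan says.** Absolute oral bioavailability is a primary endpoint (SAP 1.2.1 and 5.2.1). Table 6 in SAP 5.2.2 models it with "Fixed effect : Treatment (IV dose/Oral dose in Period1") and "Random Effect : Subject". It adds "The Kenward and Roger method for approximating the denominator degrees of freedom" and states that the "associated 90% confidence interval for the contrast (test-reference) will be constructed using the residual variance". The response is the log of AUC(0-t) or AUC(0-inf), and "Dose normalized PK parameters should be used for the analysis".

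Table 6 does not require both an oral and an IV AUC from each man, and it does not say what happens if the subject variance is estimated as zero. The PK analysis set (SAP 4) needs only one non-missing PK value. The analysis goes ahead if plasma profiles are well defined, which is not a rule about pairs.

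Two nearby provisions matter:

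- Table 7 (SAP 5.4.2, exploratory relative bioavailability) has a paired-t fallback in men who completed both periods. Its trigger is "In case there is a problem with model convergence". Table 6 has no such fallback.
- Per-man F is also planned. Protocol 9.4.3 estimates F for each participant, SAP Table 4 defines F(0-inf) and F(0-t) per subject, and SAP 5.2.2 summarises and lists F.

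**The concern.** SAP 3 supports the small sample partly by saying that giving IV and oral together "inherently reduces variability in the parameters determined, versus a cross-over design for absolute bioavailability assessment". That gain comes from the within-man pair, so the interval for F should keep the pair in every data set. With 4 to 6 men the subject variance is poorly estimated and can come out as zero. The fit then still counts as a valid solution, but it treats the oral and IV values as if they came from different men.

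An oral AUC without its IV partner is a second gap. The CLr row of Table 4, which concerns the IV analyte, already provides for a plasma AUC(0-inf) that "is not calculable, then" replaced by AUC(0-t). The infusion starts 5 h after the oral dose (protocol 4.1.1), so a man could also be lost in between. The model-based F and the summarised per-subject F could then come from different men, and nothing says which of the two governs.

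**Working it through.** **Inputs from the documents.** n = 4 to 6, two-sided 90% CI, and the Table 6 model. No sample-size calculation, expected F or variability is given, so there is no stated figure to reproduce. F is taken as oral over IV, as in Table 4.

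**Complete pairs, algebra.** For each man let d = log(oral AUC/dose) − log(IV AUC/dose). Let s²(iv) and s²(po) be the sample variances of the two logs and c their sample covariance.

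- REML estimate of the subject variance: c if c > 0, otherwise 0 when bounded.
- If c > 0: residual variance = [s²(iv) + s²(po) − 2c]/2, so SE = SD(d)/√n on n−1 df. This is the paired t-interval.
- If c ≤ 0: residual variance = [s²(iv) + s²(po)]/2, so SE = √{[s²(iv) + s²(po)]/n} on 2(n−1) df. This is the unpaired interval.

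The point estimate is mean(d) in both cases. When c ≤ 0 the model SE cannot exceed the paired SE, and the t multiplier also falls: 2.353 to 1.943 (n=4), 2.132 to 1.860 (n=5), 2.015 to 1.812 (n=6). The model interval is therefore always the narrower one on the log scale.

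**Invented example, n=4.** Log IV values 0, 0.3, −0.2, 0.1; log oral values −1.2, −1.6, −0.9, −1.3. Then s²(iv) = 0.0433, s²(po) = 0.0833, c = −0.060 and mean(d) = −1.30 (F = 0.273).

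- Paired: SE = √(0.2467/4) = 0.248; 90% CI exp(−1.30 ± 2.353 × 0.248) = 0.152 to 0.489.
- Table 6: SE = √(0.1267/4) = 0.178; 90% CI exp(−1.30 ± 1.943 × 0.178) = 0.193 to 0.385.

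In a six-man example with c > 0, both methods gave F 0.299 with CI 0.277 to 0.322.

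**How often.** Assumed: independent log-normal CL and F, CV of CL 20%, CV of F 20, 40 or 60%, and error SD 0.05 on each log AUC. There were 400,000 simulated trials per row.

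| n | CV of F | IV/oral correlation | Subject variance zero | Median width vs paired | Overall coverage, Table 6 | Coverage within zero-variance trials: Table 6 / paired |
|---|---|---|---|---|---|---|
| 6 | 20% | 0.67 | 5% | 0.83 | 89.8% | 93% / 97% |
| 6 | 40% | 0.44 | 16% | 0.84 | 89.2% | 90% / 95% |
| 6 | 60% | 0.32 | 24% | 0.84 | 88.8% | 89% / 94% |
| 4 | 20% | 0.67 | 11% | 0.74 | 89.4% | 92% / 97% |
| 4 | 40% | 0.44 | 23% | 0.74 | 88.5% | 89% / 96% |
| 4 | 60% | 0.32 | 30% | 0.75 | 87.9% | 87% / 94% |

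Overall coverage of the paired interval was 90.0% in every row. At a correlation of 0.87 the zero-variance case falls to 0.5% (n=6) and 2.7% (n=4).

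**Oral-only man.** With m complete pairs, k oral-only men and fitted correlation ρ, the oral-only mean enters the treatment contrast with weight (1−ρ) × k/(m+k). For m=5, k=1 the weight is 0.083 at ρ=0.5, 0.050 at ρ=0.7 and 0.017 at ρ=0.9. If his oral AUC is half that of the others, F is multiplied by 0.5 to the power of that weight: 0.94, 0.97 and 0.99. At ρ=0, which is the zero-variance case, the factor is 0.89. A complete-pair analysis gives him weight zero.

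**The case against.** A reader might infer that the plan gives up the within-man pair in general. It does not. In the regular case Table 6 is the paired analysis, and the per-subject F of Table 4 is listed and summarised whatever the model does. An oral-only man cannot shift that summary.

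A reader might also infer that slow eliminators bias F, because they would be the ones without an IV AUC(0-inf). The documents do not support this. The same man's oral AUC(0-inf) faces the same slow terminal phase over the same 168 h, so both may be lost. If low microdose concentrations were the cause, fast eliminators might be the ones lost. AUC(0-t) is analysed in parallel and needs no extrapolation. The CLr row is a contingency, not a forecast.

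It is fair to add that the narrower interval is not badly wrong. Within zero-variance trials it covers about 87 to 93%, while the paired one covers 94 to 97%. The problem is frequent only where the IV/oral correlation is low, and the clearance that both AUCs share in one period favours a higher one. Table 6 does not name the estimation method, so the zero bound is an assumption. If the software kept n−1 df at the bound, less coverage would be lost. Table 6 also allows data-based adjustments to the model. SAP 2 has no hypothesis, and SAP 3 puts industry practice ahead of the pairing argument.

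These points limit the size of the problem. They do not close the gap: a zero variance is not in itself a convergence failure, and an unspecified adjustment made after seeing 4 to 6 men's data does not replace a rule.

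**Conclusion.** The point holds as a gap in specification with a modest effect. In some data sets of 4 to 6 men, Table 6 would report an unpaired 90% CI, at the median 16 to 17% narrower than the paired one with six men and 25 to 26% narrower with four. Under the assumed CVs the loss in overall coverage is about 0.2 to 1.2 percentage points at n=6 and 0.6 to 2.1 at n=4. With complete pairs the estimate of F does not move. With one oral-only man added to five pairs, it moves by about 1 to 6% for correlations of 0.9 to 0.5, if his AUC is half that of the others. All of these sizes rest on assumed variability and on bounded REML. The gap itself rests only on the text of Table 6.

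**What to change.** In SAP Table 6:

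- Restrict the analysis to men with both Period 1 dose-normalised AUCs, separately for AUC(0-t) and AUC(0-inf), and state the number of pairs.
- Compute log(F_i) for each man, average it, take the 90% t-interval on n−1 df, and exponentiate. Fitting subject as a fixed effect gives the same result.
- List men with only one of the two AUCs, but do not model them.

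In Table 7, let the existing paired-t fallback also apply when the subject variance is estimated as zero.

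Protocol 8.5.4 treats a man who vomits within 4 h of the oral dose as not evaluable, while the SAP's PK set does not exclude him. The two passages should be reconciled, so that it is clear whether his plasma data enter the PK analyses.

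The cost is SAP wording and a simpler program, with no new data. Results are unchanged when pairs are complete and the subject variance is positive. The downsides are a wider CI in the zero-variance case and no contribution to F from men with a single AUC.

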9.4.3. Pharmacokinetic Analyses

Plasma GSK3640254 concentration-time data will be listed for each participant and summarised by treatment and planned sampling time. [¹⁴C]-GSK3640254 and radioactivity concentrations in whole blood and plasma will be reported similarly. Individual participant, mean and median plasma GSK3640254, [¹⁴C]-GSK3640254, and total radioactivity concentration-time profiles will be plotted for each treatment on both a linear and semi-log scale.

Pharmacokinetic analysis will be performed by or under the direct auspices of Clinical Pharmacology Modelling & Simulation, GSK. Plasma GSK3640254, [¹⁴C]-GSK3640254, and total radioactivity concentration-time data will be analysed by non-compartmental methods with WinNonlin Version 6.3 or above. Calculations will be based on the actual sampling times recorded during the study. From the plasma concentration-time data the following pharmacokinetic parameters will be determined, for GSK3640254, [¹⁴C]-GSK3640254, and total radioactivity (whole blood and plasma) as data permits: maximum observed plasma concentration (C_{max}), time to C_{max} (t_{max}), AUC(0-t) and AUC(0-inf), terminal phase rate constant (λ_z), and apparent terminal phase half-life ($t_{1/2}$) following oral and IV dosing. Additionally, V_{ss} , CL_r , and CL will be derived following IV dosing and CL/F and V_z/F will be derived following oral dosing. These parameters will be summarised descriptively.

Absolute bioavailability will be estimated for oral dose for each participant and will be summarized.

Derivation of the urine and fecal radioactivity parameters will be through support provided by CRO partners. The following radioactivity parameters will be determined from the urine and fecal radiolabelled drug-related material (total radioactivity) data, and will be listed and summarised by treatment:

- Percentage excreted in urine (Fe%[urine]) within each collection period and cumulative urinary recovery and fraction excreted over the total collection period.
- Percentage excreted in feces (Fe%[fecal]) with each collection period and cumulative fecal recovery and fraction excreted over the total collection period and cumulatively over the collection period.

- Total excretion (sum of urine and fecal excretion), Fe% [total] will be calculated by collection interval for each participant.

The urine, fecal and total radioactivity parameters will be listed, summarised and plotted, as appropriate.

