ML(iv)	
Metabolite load following intravenous administration, calculated as:
 $ML(iv) = \frac{[\text{Total Radioactivity AUC}(0 - \infty) - [^{14}\text{C}]GSK3640254 \text{ AUC}(0 - \infty)]}{\text{Total Radioactivity AUC}(0 - \infty)}$ 
Treatment Period 1

ML(po)	
Metabolite load following oral administration, calculated as:
 $ML(po) = \frac{[\text{Total Radioactivity AUC}(0 - \infty) - GSK3640254 \text{ AUC}(0 - \infty)]}{\text{Total Radioactivity AUC}(0 - \infty)}$ 
Treatment Period 2
 
Note: GSK3640254 AUC(0-∞) may be updated depending on the sample analysis conducted but refers to the parent GSK3640254 from oral dose

Fg	
Fraction metabolized by gut wall as a fraction of the oral dose, calculated as:
 $Fg = 1 - [ML(po) - ML(iv)]$

CONFIDENTIAL

Statistical Analysis Plan 213051

Parameter	Parameter Description
$CL_{h,iv,blood}$	
Hepatic blood clearance, calculated as:
 $CL_{h,iv,blood} = CL_{h,iv,plasma} * \text{blood to plasma ratio}$ 
Where $CL_{h,iv,plasma}$ is the hepatic plasma clearance calculated as:
 $CL_{h,iv,plasma} = CL - CL_r$
E_h	
Hepatic extraction ratio, calculated as:
 $E_H = CL_{h,iv,blood} / Q_h$ 
Where Q_h = hepatic blood flow (literature value of 1660 mL/min, Edginton, 2006)
 
Note: if assumption that hepatic CL accounts for 100% of the clearance (i.e. CL_r is negligible), then $E_h = CL * \text{blood to plasma ratio} * Q_h$

F_h	$F_h = 1 - E_h$
F_a	
Fraction absorbed following an oral dose, calculated as follows
 $F_a = \frac{F(0 - \infty)] / (1 - E_H)}{F_g}$
Dose(iv)	Radiometric IV dose calculated by Covance
Dose(oral)	Radiometric oral dose calculated by Covance
$F(0-\infty)$	
Oral absolute bioavailability based on $AUC(0-\infty)$, calculated as:
 $F(0 - \infty) = \frac{GSK3640254 \text{ AUC}(0 - \infty)(\text{oral})}{\text{Dose}(\text{oral}) \frac{\text{Dose}(\text{iv})}{[14C]GSK3640254 \text{ AUC}(0 - \infty)(\text{iv})}}$ 
Per Subject

CONFIDENTIAL

Statistical Analysis Plan 213051

Parameter	Parameter Description
	Note: Radiometric dose will be used for IV. GSK3640254 AUC(0-∞) (Oral) refers to the parent GSK3640254 from oral dose, but may be updated depending on the sample analysis

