F(0-t)	
Oral absolute bioavailability based on AUC(0-t), calculated as:
 $F(0-t) = \frac{\text{GSK3640254 AUC}(0-t)(\text{oral})}{\frac{\text{Dose}(\text{oral})}{\text{Dose}(\text{iv})} * \frac{[14C]\text{GSK3640254 AUC}(0-t)(\text{iv})}{[14C]\text{GSK3640254 AUC}(0-t)(\text{iv})}}$ 
Per Subject
 
Note: Radiometric dose will be used for IV. GSK3640254 AUC(0-t) (Oral) refers to the parent GSK3640254 from oral dose, but may be updated depending on the sample analysis

CL/F	
Apparent oral clearance, calculated as:
 $CL/F = \frac{\text{Dose}}{AUC(0-\infty)}$
Vz/F	
Apparent volume of distribution based on the terminal phase
 $Vz/F = \frac{\text{Dose}}{[\lambda_z * AUC(0-\infty)]}$
GSK3640254/ Total radioactivity ratio for Cmax	
Cmax Ratio = Exp {[log_e(GSK3640254 Cmax)] - [log_e(Total radioactivity Cmax)]}
 
Per subject for radiolabelled oral dose. GSK3640254 may be updated depending on the sample analysis conducted but refers to the parent GSK3640254 from oral dose

GSK3640254/ Total radioactivity ratio for AUC(0-∞)	
Cmax Ratio = Exp {[log_e(GSK3640254 AUC(0-∞))] - [log_e(Total radioactivity AUC(0-∞))]}
 
Per subject for radiolabelled oral dose. GSK3640254 may be updated depending on the sample analysis conducted but refers to the parent GSK3640254 from oral dose

GSK3640254/ Total radioactivity	
Cmax Ratio = Exp {[log_e(GSK3640254 AUC(0-t))] - [log_e(Total radioactivity AUC(0-t))]}

CONFIDENTIAL

Statistical Analysis Plan 213051

Parameter	Parameter Description
ratio for AUC(0-t)	Per subject for radiolabelled oral dose. GSK3640254 may be updated depending on the sample analysis conducted but refers to the parent GSK3640254 from oral dose
[¹⁴ C]-GSK3640254/ Total radioactivity ratio for Cmax	Cmax Ratio = $\text{Exp} \{[\log_e([\sup{14}\text{C}]\text{-GSK3640254 Cmax}) - [\log_e(\text{Total radioactivity Cmax})]]\}$ Per subject for radiolabelled IV dose
[¹⁴ C]-GSK3640254/ Total radioactivity ratio for AUC(0-∞)	Cmax Ratio = $\text{Exp} \{[\log_e([\sup{14}\text{C}]\text{-GSK3640254 AUC}(0-\infty)) - [\log_e(\text{Total radioactivity AUC}(0-\infty))]]\}$ Per subject for radiolabelled IV dose
[¹⁴ C]-GSK3640254/ Total radioactivity ratio for AUC(0-t)	Cmax Ratio = $\text{Exp} \{[\log_e([\sup{14}\text{C}]\text{-GSK3640254 AUC}(0-t)) - [\log_e(\text{Total radioactivity AUC}(0-t))]]\}$ Per subject for radiolabelled IV dose

Notes:

- Additional parameters may be included as required

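### SAP Table 6 reports the dose-normalised IV/oral AUC ratio as absolute bioavailability F; that ratio is 1/F

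*SAP*

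**What the plan says.** SAP Table 6 (section 5.2.2) fits a mixed model to log-transformed AUC(0-t) and AUC(0-∞) from Period 1, with treatment (IV or oral) as fixed effect and subject as random effect. The inputs are dose-normalised: "PK parameters should be divided by corresponding dose". On the comparison it says "associated 90% confidence interval for the contrast (test-reference) will be constructed using the residual variance", without naming either route as test or reference.

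The results part of the table gives the direction twice. The estimate and interval are described as "Point estimates (Absolute Bioavailability of GSK3640254) and associated 90% confidence interval for the ratio IV dose/Oral dose", and the figures as "Plots showing the adjusted geometric mean ratio(F) of IV dose to Oral dose in Period1".

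Elsewhere F points the other way:

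- The objective and endpoint (SAP 1.2.1 and 5.2.1) are absolute oral bioavailability.
- SAP Table 4 has per-participant rows such as "Oral absolute bioavailability based on AUC(0-t), calculated as", with the oral parent AUC in the numerator.
- Table 4 obtains Fa by dividing that F by (1 − Eh) and by Fg.
- Protocol 9.4.3 says "Absolute bioavailability will be estimated for oral dose for each participant and will be summarized".

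Nothing in either document inverts the Table 6 ratio or redefines F as IV over oral.

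**The concern.** Absolute bioavailability is dose-normalised oral AUC divided by dose-normalised IV AUC. Table 6 attaches the name and the symbol F to the opposite ratio. A programmer working from the SAP would produce a table and figures showing 1/F under the label F, next to a listing and summary of per-participant F that runs the other way.

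A primary endpoint is affected. Reversing the output after the data are seen would depart from the written analysis unless the SAP is corrected first. A low F would give an obviously impossible value and be caught. An F nearer 1 would give a reversed interval that can include 1 and look credible.

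**Working it through.** **There is no planned figure to reproduce.** The SAP gives no expected F, no variability and no formal sample size calculation. The check is algebraic, followed by illustrations.

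**Direction.** Let CL be clearance, and D_iv and D_po the doses.

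- AUC_iv = D_iv / CL
- AUC_po = F × D_po / CL
- Dose-normalised oral/IV = (F/CL) / (1/CL) = F
- Dose-normalised IV/oral = (1/CL) / (F/CL) = 1/F

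Doses and clearance cancel, so this holds for the 200 mg tablet with the 100 µg infusion and for any clearance.

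**Point estimates.** All F values are illustrative. 0.15 is the conservative planning assumption in protocol 4.3, not an expected result.

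| True F | Reported under Table 6 (1/F) |
|---|---|
| 0.15 | 6.67 |
| 0.30 | 3.33 |
| 0.50 | 2.00 |
| 0.80 | 1.25 |
| 1.00 | 1.00 |

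**Intervals.** When every participant contributes both routes, the mixed-model contrast has the same interval as a paired t analysis. The 90% CI is F × exp(±h), with h = t(0.95, n−1) × √ln(1+CV²) × √(2/n). The within-subject CV is assumed at 20% and 30%. The n of 6 (planned enrolment) and 4 (minimum completers) come from SAP 1.3.

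- CV 20%, n = 6: h = 2.015 × 0.198 × 0.577 = 0.230
- CV 20%, n = 4: h = 2.353 × 0.198 × 0.707 = 0.330
- CV 30%, n = 6: h = 2.015 × 0.294 × 0.577 = 0.342

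| CV | n | F (90% CI) | As Table 6 would report it |
|---|---|---|---|
| 20% | 6 | 0.30 (0.238–0.378) | 3.33 (2.65–4.20) |
| 20% | 6 | 0.80 (0.635–1.007) | 1.25 (0.99–1.57) |
| 20% | 4 | 0.30 (0.216–0.417) | 3.33 (2.40–4.63) |
| 30% | 6 | 0.30 (0.213–0.422) | 3.33 (2.37–4.69) |

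**What does not change.** In one simulated paired data set (n = 6, true F = 0.15), oral minus IV gave 0.142 (0.133–0.151) and IV minus oral gave 7.06 (6.65–7.51). %CVw was 5.2 both ways. Reversing the contrast swaps and inverts the limits and leaves the residual variance alone.

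**Orientation of F in Table 4.** The stacked fractions in the F rows are broken in the extracted text, which I do not count as an error. I rely on three things that survive: the row name, the oral AUC in the numerator, and the Fa derivation, which makes sense only if F is the oral fraction.

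**A separate ambiguity in Table 4.** Dose(oral) is defined as "Radiometric oral dose calculated by Covance", but the Period 1 tablet is unlabelled (SAP 5.2). The F rows name no period, and their notes say only "Radiometric dose will be used for IV". SAP Table 5 uses the radiometric oral dose for Period 2. This does not affect the Table 6 estimate or interval.

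**The case against.** The strongest reply is that little is at stake. The protocol asks only for per-participant bioavailability, summarised; Table 4 and the text of SAP 5.2.2 deliver that, and Fa uses the per-participant value. The Table 6 model is run only if the profiles are adequate. There is no hypothesis and no success rule for F. A reader can recover F by taking reciprocals, and at an F of 0.15 the reported 6.67 would be recognised at once. Since the endpoint is oral bioavailability, a programmer may naturally take oral as the test treatment. Display details are left to the Output and Programming Specification, which is not available here.

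Most of this stands as a limit on the damage. The F values and CVs above are illustrations and do not predict harm. The Table 4 equations also have to be read through a damaged layout, but the labelling error does not depend on them: the Table 6 wording and the endpoint are enough.

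It does not remove the error. The IV/oral wording in the fixed-effect line could be a list of factor levels, but the two results bullets cannot be read that way, because they state a ratio and the second attaches the symbol F to it. It is not the dose-correction factor either, since the plot bullet describes geometric mean ratios of AUC. The contrast line is silent on direction, so the only direction Table 6 states is the wrong one.

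**Conclusion.** The concern holds. As written, Table 6 would report the reciprocal of a primary endpoint, with its 90% CI and plots, under the name of that endpoint. The algebra needs no assumption about dose, clearance or variability and applies to any F other than 1. The size depends on F: a factor of 1/F², so an F of 0.80 is overstated by 1.25/0.80 = 1.56 and an F of 0.30 by 3.33/0.30 = 11.1. The intervals shown assume the stated CVs and complete pairs.

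The model, the confidence level, %CVw and precision are unaffected, as are the per-participant F, Fa, Fh and Fg. It should be corrected before the analysis is run because the quantity specified is wrong and the correction is nearly free.

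**What to change.** In SAP Table 6:

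1. Define the contrast as test = Period 1 oral tablet and reference = Period 1 IV dose.
2. In the results bullet, report the dose-normalised geometric mean ratio oral/IV with its 90% CI as F.
3. In the plot bullet, plot the same oral/IV ratio.

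In SAP Table 4, as a secondary clarification, add a note that F uses the Period 1 oral parent AUC (LC-MS/MS) with the administered tablet dose, and that the radiometric oral dose is for Period 2 parameters.

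The cost is SAP wording only: two bullets, the contrast definition and one note. Design, sampling and model stay as they are. The Output and Programming Specification should be checked for the same direction.
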